4.1. Study Treatments

Study drug will be administered orally as 3 tablets twice daily (5 mg CCX140-B tablets, matched placebo, or combination) for up to 12 weeks in a double-blind manner.

Table 1: CCX140-B for the Four Study Groups

| Group | 12 weeks | | | |
|--------------|--|---|----------------------------|-----------------------------|
| | 5 mg CCX140-B QD | 10 mg CCX140-B BID | 15 mg CCX140-B BID | Placebo |
| Morning dose | 1 x 5 mg tablet + 2 placebo tablets orally | 2 x 5 mg tablets+ 1 placebo tablet orally | 3 x 5 mg tablets orally | 3 placebo tablets orally |
| Evening dose | 3 placebo tablets orally | 2 x 5 mg tablets+ 1 placebo tablet orally | 3 x 5 mg tablets orally | 3 placebo tablets orally |

4.2. Dose Modification Guidelines

The DMC will be responsible for reviewing safety data throughout the course of the study. In the event the DMC has a strong indication that there are significant dose-related adverse events the DMC can make the recommendation to discontinue enrollment to the affected arm and to step-down all subjects to the next lower dose arm. In addition to the planned data reviews, the DMC charter will include pre-specified rules that trigger an Ad Hoc review of data by un-blinded treatment group.

Subjects participating in the Open-Label Extension will be switched over to the highest safest dose of the CCX140-B.

4.2.1. Stopping Guidelines

An independent Data Monitoring Committee (DMC) will be responsible for reviewing safety data throughout the course of the study. Among other responsibilities, the DMC is tasked with implementing dose modification guidelines to assure the safety of all study participants.

Guidelines will be defined for stopping the study, halting enrollment or halting treatment based on safety events occurring in more than 1 subject. General dose modification guidelines for individuals are provided below.

Table 2: Dose Modification Guidelines for Single Subjects

| Assessment | Event | Timing | Response |
|---------------------------------------|---|--|-------------------------------------|
| Serum Creatinine | 50% increase from baseline value | If confirmed by repeat measurement after 2 weeks | Discontinue treatment with CCX140-B |
| Urine Protein:Creatinine ratio (UPCR) | If baseline UPCR < 6.0 g/g an increase of >3.0 g/g; if UPCR \geq 6.0 g/g an increase of 50% | If confirmed by repeat measurement after 2 weeks | Discontinue treatment with CCX140-B |

| Assessment | Event | Timing | Response |
|-----------------------------------|--|--|--|
| ALT, AST | ALT or AST ≥ 8 x ULN | Retest within 72 hours (ALT, ASP, ALP and Total Bilirubin should all be re-tested) | If confirmed, discontinue treatment with CCX140-B |
| ALT, AST | ALT or AST ≥ 5 x ULN for more than 2 weeks | Retest within 72 hours and then 2-3 times per week (ALT, ASP, ALP and Total Bilirubin should all be re-tested) | If confirmed, discontinue treatment with CCX140-B |
| ALT, AST, Total Bilirubin and INR | ALT or AST ≥ 3 x ULN and either Total Bilirubin > 2 ULN or INR > 1.5 | Retest within 72 hours (ALT, ASP, ALP, Total Bilirubin and INR should all be re-tested) | If confirmed, discontinue treatment with CCX140-B |
| ALT, AST | ALT or AST ≥ 3 x ULN with the appearance of fatigue, nausea, vomiting, right upper quadrant pain or tenderness, fever, rash and /or eosinophilia ($>5\%$) | | Discontinue treatment with CCX140-B |
| LDH | LDH ≥ 2 times upper limit of normal, and confirmed to not be related to specimen handling | Halt treatment then reassess after 2 weeks | If within normal range, continue to treat at reduced dose, defined as the next lower dose. Otherwise, contact Medical Monitor to discuss next steps |
| Anemia | Hemoglobin reduced from baseline by ≥ 2 g/dL and deemed clinically significant by the PI | Halt treatment then reassess after 2 weeks | If normal, continue to treat at reduced dose, defined as next lower dose. Otherwise, contact Medical Monitor to discuss next steps |
| Reticulocyte Count | Increase from baseline in reticulocyte count by ≥ 2 units (% of RBC) that is not otherwise explained | Halt treatment then reassess after 2 weeks | If within normal range for the hematocrit, continue to treat at reduced dose, defined as next lower dose. Otherwise, contact Medical Monitor to discuss next steps |

| Assessment | Event | Timing | Response |
|-------------------------------------|---|--|---|
| Peripheral Neuropathy | ≥ moderate symptoms limiting (limiting instrumental activities of daily living) or asymptomatic (based on diagnostic evaluation only) and deemed clinically significant by the PI | Halt treatment then reassess after 2 weeks | Contact Medical Monitor to discuss next steps |
| Other Clinically Significant Events | Any adverse events assessed as moderate, related to study drug, and clinically significant | Halt treatment then reassess after 2 weeks | Contact Medical Monitor to discuss next steps |

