- The AIDS Clinical Trials Group Brief Peripheral Neuropathy Screening Tool Brief Peripheral Neuropathy Screening Tool (ACTG-BPNST) to assess early evidence of neuropathy;
- Monitoring for adverse events of infection;
- Alkaline phosphatase, ALT, AST and bilirubin (**total and direct**); to assess for evidence of drug induced liver injury.

For assessment of pharmacokinetics, study procedures will include

- Seven blood samples collected over 6 hours on Study Day 1 and at steady state (Study Day 15, or within 2 weeks thereafter) to assess AUC_{0-6} following the first administration of study drug, and at steady state;
- Assessment of C_{min} at intervals to ensure that exposure is within the projected range, with adequate safety margin based on the NOAEL established in preclinical toxicology;
- Upon discontinuation of treatment for any reason, collection of blood at 2 days, 7 days and 14 days following discontinuation to assess elimination.

All study procedures are presented in the [Time and Events table](#).

Subjects who are using an angiotensin converting enzyme (ACE) inhibitor, angiotensin receptor blocker (ARB) or other blocker of the renin angiotensin aldosterone system (RAAS), or who are using glucocorticoids, a calcineurin inhibitor or other immunomodulatory or immunosuppressive

[figure not shown]
therapy, should be on a stable dose for at least 4 weeks prior to screening. The dose of these medications must be kept constant over the course of the study in order to prevent undue influence of changes in these medications on the efficacy and safety assessments except when adjustment is required for patient well-being. The investigator must also attempt to keep doses of other medications, and lipid-lowering medications fixed throughout the blinded study period in order to prevent undue influence of changes in these medications on the efficacy and safety assessments.

Subjects who experience deteriorating renal function based on an increase in serum creatinine of at least 50% (confirmed by a repeat measurement after 2 weeks) which is otherwise not explained (e.g., dehydration, new medication), or increase in UPCR of >3.0 g/g (confirmed by a repeat measurement after 2 weeks) during the 12-week treatment period, will exit the treatment phase of the study and be treated at the discretion of the treating physician. All subjects who discontinue treatment will remain in the study for follow up and outcome recording.

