5.5. Removal of Subjects from Therapy of Assessment

Investigators must clearly distinguish between study drug treatment discontinuation and study withdrawal. Subjects who discontinue study drug treatment or who initiate medication changes (including those prohibited by the protocol) will not be automatically withdrawn from the study, but all efforts must be made to continue to follow the subjects for all regularly scheduled visits. The Medical Monitor should be contacted to determine how to address the specific situation.

Investigators must take appropriate measures to make sure that subjects are motivated to comply with all requirements of the protocol in order to minimize the amount of missing data. Subjects who discontinue study treatment early or initiate medication changes (including those prohibited by the protocol) should continue to be followed for all regularly scheduled visits for safety and efficacy assessments. Investigators and their staff must take measures to actively maintain contact with their subjects in the study, such as telephone calls, texts, or emails between visits, and offers for transportation support to visit the study site.

5.5.1. Subjects may be withdrawn from the study for the following reasons:

1. Subject withdrawal of consent to contribute additional outcome information;
2. Subject non-compliance with dosing or diary completion;
3. Loss to follow-up;
4. Sponsor's decision to terminate the study.

5.5.2. Subjects may discontinue study drug treatment for any of the following reasons:

1. Subject withdrawal of consent;
2. The Investigator may discontinue study drug treatment if, in his/her clinical judgment, it is in the best interest of the subject;
3. The Sponsor may request discontinuation of study drug treatment for safety reasons or non-compliance with treatment;
4. The Sponsor may request discontinuation of study drug treatment due to new or increased glucocorticoid/immunosuppressant treatment.

In the event of early withdrawal from the study, the tests and evaluations listed for the Early Termination visit in [Section 7.14](#) will be performed, whenever possible. Data collected at this visit will be designated as an "Early Termination" visit in the EDC. The Sponsor should be notified of all study drug treatment and study withdrawals in a timely manner.

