8.2.3.1. Adverse Event Severity Assessment

The severity of each adverse event will be determined by the investigator using the following scale:

- Mild (Grade 1): no limitation of usual activities
- Moderate (Grade 2): some limitation of usual activities
- Severe (Grade 3): inability to carry out usual activities
- Life-threatening (Grade 4): an immediate risk of death
- Death (Grade 5)

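### The catch-all row of Table 2 halts drug for moderate related events but, as written, not for severe or life-threatening ones

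*Protocol*

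**What the plan says.** Section 4.2.1 gives individual dose-modification guidance in Table 2. Ten rows have specific criteria. The eleventh, for other clinically significant events, is triggered by "Any adverse events assessed as moderate, related to study drug, and clinically significant". The action is "Halt treatment then reassess after 2 weeks", followed by a discussion with the Medical Monitor.

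Section 8.2.3.1 sets the severity scale that investigators use. Two adjacent entries are "Moderate (Grade 2): some limitation of usual activities" and "Severe (Grade 3): inability to carry out usual activities". Life-threatening is Grade 4 and death is Grade 5.

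Section 4 names the adverse events of special interest through the procedures used to assess them: hemolysis, neuropathy, infection ("Monitoring for adverse events of infection") and drug-induced liver injury.

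Outside Table 2, section 5.5.2 provides that "The Investigator may discontinue study drug treatment if, in his/her clinical judgment, it is in the best interest of the subject" and that "The Sponsor may request discontinuation of study drug treatment for safety reasons or non-compliance with treatment". Section 4.2.1 also promises separate guidelines for stopping the study, halting enrollment or "halting treatment based on safety events occurring in more than 1 subject".

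**The concern.** A catch-all stopping row should set a floor: this grade and anything worse. This one names a single grade. Followed literally, it inverts the safety logic. A related, clinically significant Grade 2 event leads to a prescribed halt, but a more severe event of the same kind leads to none if it meets no specific row.

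The row matters because it alone covers events that were not foreseen. Section 2.4.1 says the drug had not previously been given in biopsy-proven FSGS. Section 6.4 projects total exposure at 15 mg twice daily at 3.07 times that seen with 10 mg daily in diabetic nephropathy. Section 6.8 allows background glucocorticoids, immunosuppressants and calcineurin inhibitors, so serious infection is a realistic possibility. What is at stake is consistent protection of individual subjects across the approximately 40 planned sites. The efficacy inference is not affected.

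**Working it through.** No arithmetic beyond counting applies, and the plan states no figure to reproduce. The check is a reading of every Table 2 row against the severity scale, then a search for any other provision that would require a halt.

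**Step 1: what the rows cover.**

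| Table 2 criterion | Rows |
|---|---|
| Serum creatinine | 1 |
| UPCR | 1 |
| Liver (ALT/AST alone, or with bilirubin, INR or symptoms) | 4 |
| LDH | 1 |
| Hemoglobin | 1 |
| Reticulocytes | 1 |
| Peripheral neuropathy | 1 |
| Other clinically significant events | 1 |

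Specific rows: 1 + 1 + 4 + 1 + 1 + 1 + 1 = 10. With the catch-all, 11.

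**Step 2: events of special interest matched to specific rows.** Hemolysis has 3 (LDH, hemoglobin, reticulocytes), liver injury 4, neuropathy 1 and infection 0. Three of the four kinds have their own rows. Infection reaches a halt only through the catch-all, unless it happens also to move a listed laboratory value or cause neuropathy.

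**Step 3: apply the catch-all literally to a related, clinically significant event that meets no specific row.**

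| Grade in 8.2.3.1 | Named in the row? | Table 2 halt |
|---|---|---|
| 2, moderate | Yes | Yes |
| 3, severe | No | No |
| 4, life-threatening | No | No |

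Of the three non-fatal grades from moderate upward, the row names one.

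**Step 4: is a threshold implied by the table's style?** The neuropathy row, directly above, puts a ≥ sign before moderate. The LDH, hemoglobin, reticulocyte and liver rows also carry ≥ signs. The table therefore marks a floor where it means one, and the catch-all row has no such mark.

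**Step 5: does anything else require a halt for that one subject?**

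- Section 5.5.2 is permissive for both investigator and sponsor.
- The group guidelines in section 4.2.1 concern events in more than one subject.
- Section 4.2 provides for ad hoc DMC review under charter rules, by unblinded treatment group.
- Section 8.2.5 requires SAE reporting within 24 hours, which is notification. A Grade 3 event need not be an SAE, because inability to carry out usual activities is not itself a seriousness criterion in section 8.2.3.3.
- Section 5.4 considers new infections only at entry to the open-label period.
- SAP section 3.6.1 repeats the severity scale and adds no stopping rule.

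None of these is a required individual halt.

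**The case against.** The best counter-argument is that the row has only one sensible reading. Section 4.2.1 presents the table as general guidance, and an investigator who stopped drug for a moderate event but continued through a life-threatening one would defeat its evident purpose. This is fair, and it is why the practical risk is low.

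Second, the difference between a prescribed halt and a discretionary one is narrower than it sounds. The row already depends on judgments of severity, relatedness and clinical significance, and it ends in a conversation with the Medical Monitor. Those who make the judgments largely hold the section 5.5.2 powers as well. That also stands: what is lost is a prescribed temporary halt with reassessment at 2 weeks, not a mandatory permanent discontinuation.

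Third, the backstops are substantial. Many severe infections would be SAEs through hospitalization, disability or the important-medical-event criterion, as well as through threat to life. The DMC sees unblinded safety data and is charged with implementing the dose-modification guidelines. Its charter and the multi-subject guidelines are not in the documents, so a single event might trigger review. This makes continued dosing by oversight unlikely, but it does not supply the missing individual rule.

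Finally, nothing in the protocol says that each event of special interest needs its own row. Agreed. The absence of an infection row is a problem only because the catch-all it relies on is incomplete.

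**Conclusion.** The concern holds as a wording error in an operative safety threshold. As written, Grades 3 and 4 are left out of the catch-all, and a related severe event outside the 10 specific rows triggers no Table 2 halt while its Grade 2 counterpart does.

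Severity is low. The conclusion rests on a literal reading, and on the cell containing no ≥ sign; the sign is present in the neighbouring rows. Sites would probably apply the row as at least moderate. The documents give no expected rate of related Grade 3 or 4 events, so no number of affected subjects can be given. There is no effect on sample size, power or type I error. It is still worth correcting, because a stopping rule should not depend on readers supplying the missing words.

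**What to change.** Change the event cell to: *Any adverse event assessed as moderate or worse (Grade ≥2), related to study drug, and clinically significant.* Keep the present response (halt, reassess after 2 weeks, contact the Medical Monitor) and state that it is the minimum action for Grades 3 and 4.

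The change is one table cell, with no added visits, tests or subjects. Because it bears on subject risk, section 11.4 requires IRB/EC approval before it takes effect, so it is best carried in an amendment made for other reasons. Meanwhile, a short clarification to sites confirming the intended reading would cover the gap.

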5. STUDY POPULATION

5.1. Size of the Population

Approximately 40 male or female adult subjects with primary or genetic FSGS (see [Section 5.2](#); for genetic variants) will be enrolled in this study. Subjects who discontinue during the first 14 days of taking study drug for reasons other than adverse events related to study drug may be replaced to ensure that sufficient data are available for assessment of safety, PK and efficacy.

5.2. Inclusion Criteria

Subjects must meet all the following inclusion criteria to enter the study:

1. Male or female subjects aged 18-75 years inclusive.
2. Urinary total protein:creatinine ratio (UPCR) ≥ 1 g protein/g creatinine at screening (or UPCR at 113 mg/mmol).
3. Diagnosis of FSGS based on at least one of the following:
 - Renal biopsy demonstrating the FSGS lesion and characteristic clinical presentation and course
 - High risk genetic variant and characteristic clinical presentation and course
4. Diagnosis of one of the following subtypes of FSGS:
 - Primary FSGS based on characteristic histopathology, medical history and clinical course, or
 - FSGS secondary to a genetic variant associated with increased risk or severity, which may include NPHS1, NPHS2, WT-1, LAMB2, CD2AP, TRPC6, ACTN4 or INF2
5. Estimated glomerular filtration rate (eGFR) >30 mL/min/1.73m², with eGFR calculated using the Chronic Kidney Disease Epidemiology Collaboration (CKD_EPI) equation (using creatinine or cystatin C)
6. The typical blood pressure of the patient should be clinically stable prior to enrollment and not exceed 145/95 mmHg.
7. If using RAAS blockers, dose must be stable for a minimum of 4 weeks prior to Screening, and projected to remain stable through Study Week 12, unless adjustment is required for management of hypertension.
8. If using immunosuppressive or immunomodulatory therapy, dose must be stable for a minimum of 4 weeks prior to Screening, and projected to remain stable through Study Week 12.
9. If using glucocorticoids, dose must be stable for a minimum of 4 weeks prior to Screening and projected to remain stable through Study Week 12.
10. Female subjects of childbearing potential may participate if adequate contraception is used during, and for at least **1 month** after last dose of study drug. Male subjects with partners of

childbearing potential may participate in the study if they had a vasectomy at least 6 months prior to randomization or if adequate contraception is used during, and for at least one month after the last dose of study drug. Adequate contraception is defined as resulting in a failure rate of less than 1% per year (combined estrogen and progestogen [oral, intravaginal, or transdermal], or progestogen-only hormonal contraception (oral, injectable, or implantable), intra-uterine device, intra-uterine hormone releasing system, bilateral tubal occlusion, vasectomized partner, or sexual abstinence). In addition, a barrier method (i.e. cervical cap, diaphragm or condom) must be used during intercourse between a male subject and a female of child-bearing potential.

11. Willing and able to give written Informed Consent and to comply with the requirements of the study protocol.
12. Judged to be otherwise fit for the study by the Investigator, based on medical history, physical examination, and clinical laboratory assessments. Subjects with clinical laboratory values that are outside of normal limits (other than those specified in the Exclusion Criteria) and/or with other abnormal clinical findings that are judged by the Investigator not to be of clinical significance, may be entered into the study.

5.3. Exclusion Criteria

1. Pregnant or nursing.
2. History of organ transplantation, including renal transplantation.
3. Currently on an organ transplant waiting list or there's a reasonable possibility of getting an organ transplant within 6 months of screening
4. Subjects **who used** rituximab or other **B-cell depleting** monoclonal antibodies within 20 weeks prior to screening are excluded while subjects **who used** rituximab or other **B-cell depleting** monoclonal antibodies prior to 20 weeks **before** screening are allowed with confirmed recovery of **the B-cell population to within normal range at the time of screening**
5. Plasmapheresis within 12 weeks prior to screening.
6. Body Mass Index (BMI) ≥ 40
7. Participated in any clinical study of an investigational product within 12 weeks prior to screening or within 5 half-lives after taking the last dose of investigational product.
8. Currently on dialysis or likely to require dialysis during the projected blinded treatment period of 12 weeks.
9. History or presence of any form of cancer within the 5 years prior to screening, with the exception of excised basal cell or squamous cell carcinoma of the skin, or carcinoma *in situ* such as cervical or breast carcinoma *in situ* that has been excised or resected completely and is without evidence of local recurrence or metastasis.
10. Positive HBV, HCV, or HIV viral screening test. Subjects who have received highly effective therapy for HCV demonstrated to have negative viral titers for at least 6 months following discontinuation of treatment, will be considered to have a negative HCV screening test.

11. Renal disease associated with disorders other than FSGS (e.g. lupus nephritis, C3 glomerulopathy, proliferative glomerulonephritis, IgA nephropathy, reflux nephropathy, surgical segmental renal ablation, sickle cell disease) that is active, or has a significant risk of progressing during the course of the study
12. Disorders other than those listed in Inclusion Criteria 4 that are associated with FSGS lesion (**i.e. secondary FSGS, such as** single kidney, surgical segmental renal ablation, sickle cell disease, diabetic nephropathy, others), **or histological collapsing variant subtypes of FSGS**
13. Evidence of tuberculosis based on interferon γ release assay (IGRA) within 6 weeks prior to screening.
14. Evidence of hepatic disease; AST, ALT, alkaline phosphatase $>3x$ ULN, or total bilirubin $>2x$ ULN or INR $>1.5 \times$ ULN at **screening** with the exception that isolated INR elevation in the absence of other significant liver enzyme abnormalities is explained by anticoagulant therapy, (e.g. warfarin).
15. Clinically significant peripheral neuropathy.
16. Hematologic abnormalities as follows: Hb <8 g/dL, platelets $<50,000$, ANC <1000 cells/ μ L) at baseline.
17. Clinically significant abnormal ECG during screening, e.g., QTcF greater than 450 msec.
18. History of alcohol or illicit drug abuse. Recreational use of cannabis is not excluded where legal.
19. History of gastrointestinal conditions that may interfere with study medication compliance, e.g., severe gastroparesis, with regurgitation of food or oral medication.
20. Known hypersensitivity to CCX140-B or inactive ingredients of the CCX140-B tablets (including microcrystalline cellulose, starch, crospovidone, magnesium stearate, silicon dioxide **or tartrazine**).
21. History or presence of systemic disorder other than FSGS that requires, or is expected to require, systemic glucocorticoids or immune modulators during the study; topical or inhaled glucocorticoids and immune modulators are not excluded.
22. History or presence of any medical condition or disease which, in the opinion of the Investigator, may place the subject at unacceptable risk for study participation.
23. Subjects taking strong CYP3A4 inducers (e.g., phenytoin, rifampicin, carbamazepine, St. John's Wort) or strong CYP3A4 inhibitors (e.g., boceprevir, clarithromycin, conivaptan, grapefruit juice, indinavir, itraconazole, ketoconazole, lopinavir/ritonavir, mibefradil, nefazodone, neflifinavir, posaconazole, ritonavir, saquinavir, telaprevir, telithromycin, and voriconazole) within two weeks prior to screening.
24. Subjects taking lithium, **pamidronate**, or interferon; subjects taking non-steroidal anti-inflammatory agents (NSAIDS) chronically (intermittent, i.e. occasional NSAIDS for pain or fever is discouraged, but is not excluded).

